#### 17. At Screening (Visit 1)

Subject who has taken antibiotics within 2 weeks of their Screening visit.

#### 18. At Baseline (Visit 2)

Subject who has taken antibiotics within 2 weeks of their Baseline visit (during the acclimatisation period).

- 19. Subject who has had a professional or self-applied tooth bleaching procedure within 8 weeks of Screening (Visit 1).
- 20. Subject who has had dental prophylaxis within 4 weeks of Screening (Visit 1).
- 21. Subject who has had treatment for periodontal disease (including surgery) within 12 months of Screening (Visit 1).
- 22. Subject who has had scaling or root planning within 3 months of Screening (Visit 1).
- 23. Subject with a tongue or lip piercing.

24. Subject with, in the opinion of the investigator or medically qualified designee, gross periodontal disease.

Property of GSK Consumer Healthcare - Confidential

May not be used, divulged, published or otherwise disclosed without the consent of GSKCH

Clinical Protocol Template v9.0

Page 24 of 73

- 25. Subject with evidence of gross intra-oral neglect or the need for extensive dental therapy.
- 26. Subject with a fixed or removable partial prosthesis which, in the opinion of the investigator or medically qualified designee, would impact study outcomes.
- 27. Subject with multiple dental implants which, in the opinion of the investigator or medically qualified designee, would impact study outcomes.
- 28. Subject with fixed or removable orthodontic braces/bands or a fixed orthodontic retainer.

### **29. SPECIFIC DENTITION EXCLUSIONS FOR 'TEST TEETH':**

- a) Tooth with evidence of current or recent caries or reported treatment of decay within 12 months of Screening (Visit 1).
- b) Tooth with exposed dentin but with deep, defective or facial restorations.
- c) Tooth with full crown or veneer.
- d) Tooth adjacent to a bridge abutment or crown which, in the opinion of the investigator or medically qualified designee, would impact study outcomes.
- e) Sensitive tooth with contributing aetiologies other than erosion, abrasion or recession to exposed dentine.
- f) Sensitive tooth, in the opinion of the investigator or medically qualified designee, not expected to respond to treatment with an anti-sensitivity toothpaste.
- 30. Subject who has previously been enrolled in this study.
- 31. Any subject who, in the opinion of the investigator or medically qualified designee, should not participate in the study.

# 5.4 Randomization Criteria

Subjects who satisfy all selection criteria will be randomized into the study. Randomisation numbers will be assigned in ascending numerical order as each subject is determined to be fully eligible.

Subjects will be stratified by the maximum Baseline Schiff sensitivity score of their two selected test teeth. The stratification factor will give rise to two strata.

- Stratum 1: Maximum Schiff sensitivity score = 2
- **Stratum 2:** Maximum Schiff sensitivity score = 3

Within each stratum, subjects will be randomized to test toothpaste, negative control or positive control with 2:2:1 allocation ratio using permuted randomised blocks (see Section 12.1).

# 5.5 Lifestyle Considerations

If, in the opinion of the investigator or medically qualified designee, a subject has not complied with a study restriction (oral hygiene, dietary or alcohol-related) prior to a study visit or cannot attend a study visit, every effort will be made to reappoint them within the permitted visit tolerances (see Schedule of Activities, Table 1-1). The reason for re-appointment will be documented in the electronic case report form (eCRF).

Property of GSK Consumer Healthcare - Confidential

May not be used, divulged, published or otherwise disclosed without the consent of GSKCH

Clinical Protocol Template v9.0

Page 25 of 73

If re-appointment is not possible, the following visit specific actions should be taken:

- **Baseline (Visit 2):** if the subject cannot be reappointed (within the 2-4 week visit tolerance), they will be withdrawn from the study. No clinical efficacy assessments will be performed. The subject may be replaced.
- Week 6 (Visit 3): if the subject cannot be reappointed (within the visit tolerance) the subject will continue in the study. No clinical efficacy assessments will be performed.
- Week 12 (Visit 4): if the subject cannot be reappointed (within the visit tolerance), they will be withdrawn from the study. No clinical efficacy assessments will be performed. The subject will not be replaced.

### 5.5.1 Oral Care Restrictions

#### For the Duration of the Study: From Screening (Visit 1) to the Subject's Last Study Visit

- Subjects should stop using their own oral care products
- Subjects should not use any other oral care products (e.g., toothpastes, toothbrushes, oral rinses, tongue cleaners, whitening/bleaching products, interdental cleaning products) than those provided during the study.

Note: Dental floss can be used but only to remove impacted food.

• Subjects should not chew gum.

#### Before a Clinical Assessment Visit: Baseline (Visit 2), Week 6 (Visit 3), Week 12 (Visit 4)

• Subjects will refrain from all oral hygiene procedures for at least 8 hours prior to their appointment (subjects will be sent a WeChat reminder the day before their appointment to remind them of this).

### 5.5.2 Dietary and Alcohol Restrictions

#### Before a Clinical Assessment Visit: Baseline (Visit 2), Week 6 (Visit 3), Week 12 (Visit 4)

• Subjects must not eat or drink for at least 2 hours before a clinical assessment visit.

*Note:* Small sips of room-temperature water are permitted to take medications or to relieve a dry mouth up to 1 hour before their appointment time

• Subjects should refrain from excessive alcohol consumption for 24 hours before a clinical assessment visit.

#### 5.5.3 Covid-19

Local Chinese guidelines and/or clinical site requirements will be followed.

#### 5.5.4 Contraception

Given the study products are commercially available toothpastes, regulated as General Goods in China, and no drugs will be utilised in this clinical study, pregnancy testing and contraceptive requirements are not deemed necessary.

Property of GSK Consumer Healthcare - Confidential

May not be used, divulged, published or otherwise disclosed without the consent of GSKCH

Clinical Protocol Template v9.0

Page 26 of 73

# 5.6 Screen Failures

Screen failures are defined as subjects who consent to participate in the clinical study but are not subsequently randomised. To ensure transparent reporting of screen failure subjects, a minimal set of screen failure information will include demography, screen failure details (e.g., withdrawal of consent), eligibility criteria, any protocol deviations and any AEs, as applicable.

Individuals who do not meet the criteria for participation in this study (screen failure) may not be re-screened.

# 5.7 Sponsor's Qualified Medical Personnel

Contact information for the sponsor's appropriately qualified and experienced medical/dental personnel or Clinical Research Scientist (CRS) for the study is documented in the Study Contact List located in the investigator site master file held at the study site.

The contact number is only to be used by study staff seeking advice on medical/dental questions or problems in the event that the established communication pathways between the study site and the sponsor's study team are not available.

The contact number is not intended for direct use by study subjects. To facilitate access to appropriately qualified sponsor personnel on study-related medical/dental questions or problems, subjects will be provided with a contact card. The contact card will provide, as a minimum, protocol identifiers, the subject's study identification number, contact information for the study site, and contact details in the event that the study site cannot be reached to provide advice on a medical question or problem identified by a healthcare professional other than the investigator.

# 5.8 Clinical Assessor Qualifications

The examiners responsible for the clinical efficacy measures will be qualified dentists, trained in the clinical assessment of DH (tactile and evaporative (air) sensitivity).

Additional qualified dentists, not trained in the clinical assessment of DH, will be permitted to conduct the oral (OST/OHT) examinations required at each study visit.

Page 27 of 73

# 6 STUDY PRODUCTS

For the purposes of this study, per International Conference on Harmonization (ICH) guidelines, and sponsor policy, study intervention is defined as any investigational intervention(s), marketed product(s), placebo, or medical device(s) intended to be administered to a study participant according to the study protocol.

# 6.1 Study Product Supplies

The following study products will be supplied by the sponsor's Clinical Supplies Department:

Product Description	Test Toothpaste	Reference Toothpaste (Positive Control)	Reference Toothpaste (Negative Control)		
Product Name**	0.454% w/w SnF2 toothpaste (Sensodyne Sensitivity & Gum*)	5.0% w/w CSPS toothpaste (Sensodyne Repair & Protect*)	Regular Fluoride toothpaste (Crest Cavity Protection Fresh Lime*)		
Fluoride Content	1100 ppm fluoride as SnF 2	1150 ppm fluoride as NaF	1150 ppm ppm fluoride as NaF		
MFC	CCI	CCI N/A			
Pack Design	One carton containing 6 over-wrapped tubes of toothpaste				
Dispensing Details	Baseline (Visit 2): One carton				
Product Application	Dose the toothbrush with a strip of toothpaste (a ribbon of toothpaste across the full brush head) on each brushing occasion				
Route of Administration	Topical Oral Use				
Usage Instructions †	Brush the two test teeth first, then the whole mouth (all teeth) for 1-timed minute, twice daily (morning and evening). After brushing, rinse once with 10 ml water using the measuring cup provided.	Brush the whole mouth (all teeth) for 1-timed minute. After brushing, rinse once with 10 ml water using the measuring cup provided.			
Return Requirements	All used/unused samples to be returned				

 Table 6-1
 Study Product Supplies

\*Chinese commercial product

† After completing each toothbrushing, subjects will be permitted to clean their tongue using the toothbrush provided (but this is not a study requirement). Tongue brushing must be completed after toothbrushing but before rinsing with 10 ml water.

Property of GSK Consumer Healthcare - Confidential

May not be used, divulged, published or otherwise disclosed without the consent of GSKCH

CCL

Clinical Protocol Template v9.0

Page 28 of 73

#### Table 6-2Acclimatization Product

Product Description	Acclimatization Toothpaste	
Product Name	Regular fluoride toothpaste (Crest Cavity Protection Fresh Lime*)	
Fluoride Content	1150ppm ppm fluoride as NaF	
MFC	N/A	
Pack Design	One carton containing 2 over-wrapped tubes of toothpaste	
Dispensing Details	Screening (Visit 1): One carton	
Product Application	Dose the toothbrush with a strip of toothpaste (a ribbon of toothpaste across the full brush head) on each brushing occasion	
Route of Administration	Topical Oral Use	
Usage Instructions †	Brush the whole mouth (all teeth) for 1-timed minute. After brushing, rinse once with 10 ml water using the measuring cup provided.	
Return Requirements         All used/unused samples to be returned		

#### \*Chinese commercial product

† On completing each toothbrushing, subjects will be permitted to clean their tongue using the toothbrush provided (but this is not a study requirement). Tongue brushing must be completed after toothbrushing but before rinsing with 10 ml water.

#### Table 6-3Sundry Items

Sundry Items to be supplied:

Item	Sumplied	Pack Design		Return/Disposal Details		
	Supplied By		Dispensing Details	Used Samples	Unused Samples	
Lion Thin Bristle		Commercial pack	Screening (Visit 1): One toothbrush	Destroy at site		
toothbrush (Chinese commercial product)			Baseline (Visit 2): One toothbrush	using site disposal		
			Week 6 (Visit 3): One toothbrush	procedures		
Countdown timer	Sponsor or designated	Commercial pack containing 1 timer	Screening (Visit 1)		Return to sponsor	
Measuring	vendor	N/A	Screening (Visit 1): 4 cups	Subject to keep		
cups			Baseline (Visit 2): 12 cups	or destroy at site using site disposal		
Opaque plastic bags		N/A	Screening (Visit 1): One bag	procedures		
			Baseline (Visit 2): One bag			

Property of GSK Consumer Healthcare - Confidential

May not be used, divulged, published or otherwise disclosed without the consent of GSKCH

Clinical Protocol Template v9.0

Page 29 of 73

For further information, please refer to the Global Clinical Supplies Packaging and Labelling Proposal. The sponsor will ensure copies of the diary (including toothpaste usage instructions), clinical assessment score sheets and Subject Contact Cards are provided to the study site.

Detailed instructions for the return of study supplies for accountability checks and subsequent destruction which will be provided by the sponsor during the study in time for study close out.

#### 6.1.1 **Dosage Form and Packaging**

All study products (test, negative control, positive control and acclimatization products) are toothpastes, intended for topical oral use, and will be applied using a manual toothbrush. All will be sourced in China.

All toothpastes will be provided to the clinical study site in their commercial packs, overwrapped in white vinyl (to mask their identity and obscure any branding) with a study label affixed. The content of the product labels will be in accordance with all applicable regulatory requirements and will be the responsibility of the sponsor's Global Clinical Supplies Department. Each study label will contain, but not be limited to, protocol number, directions for use and storage requirements.

Each subject will receive sufficient tubes of the acclimatization toothpaste and their assigned study toothpaste to cover usage during the acclimatization and treatment periods, respectively. Sundry items will be supplied in their commercial packaging for dispensing by study staff as required.

Care should be taken with the supplied products and their labels to ensure they are maintained in good condition. It is important that all labels remain intact and legible for the duration of the study. Subjects should be instructed to not remove or deface any part of the over-wrapping or study label.

All products supplied are for use only in this clinical study and should not be used for any other purpose.

#### 6.1.2 **Product Dispensing**

Subjects will be assigned to study product in accordance with the randomization schedule generated by a sponsor-approved vendor, prior to the start of the study, using validated software.

The product dispensing area will be separate from the clinical examination area. Study toothpastes will be dispensed per protocol in blinded fashion to the subject, by trained study personnel. These staff members will not be involved in any safety or clinical efficacy assessments or any other aspect of the study that could be influenced by knowing which product a subject has been assigned to. An additional member of the study staff will verify the dispensing procedure has been completed accurately for each subject.

A record of product dispensing to each subject will be maintained in the dispensing log; completion of the dispensing procedure will be recorded in the eCRF.

#### 6.2 **Administration**

Subjects will self-administer the acclimatization toothpaste (from Visit 1 to Visit 2) and their assigned study toothpaste (from Visit 2 to Visit 4) according to the usage instructions provided by study personnel at the study site and record each brushing in their diary.

Property of GSK Consumer Healthcare - Confidential

May not be used, divulged, published or otherwise disclosed without the consent of GSKCH CCI

Clinical Protocol Template v9.0

Page 30 of 73

To help ensure subjects fully understand the amount of toothpaste to use, the brushing instructions and how to complete the diary:

- Screening (Visit 1): Staff will demonstrate dispensing a full ribbon of toothpaste along the length of the toothbrush head to each qualifying subject and supervise their first brushing with the acclimatization toothpaste/diary completion at the end of the visit, after all clinical assessments have been completed.
- **Baseline (Visit 2):** Staff will check the dispensing of a full ribbon of toothpaste by each randomized subject and supervise the first brushing with their assigned study toothpaste/diary completion. Staff will clearly show subjects randomized to test toothpaste the location of their 2 test teeth prior to starting their supervised brushing.
- Week 6 (Visit 3): Staff will supervise each subject brushing with their assigned study toothpaste/completing their diary at the end of the visit, after all clinical assessments have been completed.

On-site administration of study products will be recorded in the dispensing log and the eCRF.

## 6.2.1 **Product Dosing Errors**

In this study, dosing errors may result from the administration or consumption of the wrong product, by the wrong subject, in the wrong way. Such dosing errors should be captured in the eCRF. Dosing errors are reportable irrespective of the presence of an associated AE, including:

- Dosing errors involving subject exposure to any of the study products.
- Potential dosing errors or uses outside of what was foreseen in the protocol that do or do not involve the participating subject.

If a dosing error is accompanied by an AE, as determined by the investigator or medically qualified designee, the dosing error and any associated AEs are to be captured in the eCRF AE form.

### 6.2.2 Overdose

An overdose is a deliberate or inadvertent administration of a product at an amount higher than specified in the protocol. Overdose is not likely to occur in this study.

Overdose per se is not an AE. However, any clinical sequelae of an overdose should be reported as an AE (and serious adverse event [SAE], if appropriate). For reporting, follow the AE and SAE reporting instructions.

# 6.3 Study Product Storage

The investigator or designee must confirm appropriate temperature conditions have been maintained during transit for all study products received and any discrepancies are reported and resolved before use according to the supplied shipping documentation.

The investigator, or designee, will ensure that all study products are stored in a secured area with controlled access under required storage conditions and in accordance with applicable regulatory requirements and the product labels.

Site systems must be capable of measuring and documenting (e.g., via a log), at a minimum, the daily minimum and maximum temperatures for all site storage locations, as applicable (including frozen, refrigerated, and/or room-temperature products). This should be captured

Property of GSK Consumer Healthcare - Confidential

May not be used, divulged, published or otherwise disclosed without the consent of GSKCH

Clinical Protocol Template v9.0

Page **31** of **73** 

from the time of first product receipt throughout the study. Even for continuous monitoring systems, a log or site procedure that ensures active daily evaluation for excursions should be available. The operation of the temperature-monitoring device/storage unit (e.g., refrigerator), as applicable, should be regularly inspected to ensure it is maintained in working order.

Any excursions from the product-label storage conditions should be reported to appropriate site staff upon discovery and communicated to sponsor as soon as possible. The site should actively pursue options for returning the product to the storage conditions as described in the labeling, as soon as possible. Excursions from the storage requirements, including any actions taken, must be documented as a protocol deviation and reported to the Sponsor.

Once an excursion is identified, the affected product (or products) must be quarantined and not used until the sponsor provides documentation of permission to use. Use of any of the affected product(s) prior to sponsor approval will be considered a protocol deviation.

Site staff will instruct subjects on the proper storage requirements for all take-home products.

# 6.4 Study Product Accountability

All products supplied are for use only in this clinical study and should not be used for any other purpose.

All study products must be received by a designated person at the study sites, handled and stored safely and properly, and kept in a secured location to which only the staff have access. Upon receipt, all study products should be stored according to the instructions specified on the product labels. Study products are to be dispensed by authorized site staff only to subjects enrolled in the study in accordance with the protocol.

The site must maintain adequate records documenting the receipt, use, loss, or other disposition of all the product supplies. All study products will be accounted for using the investigational/study product accountability form/record. The investigator is responsible for study product accountability, reconciliation, and record maintenance.

Subjects will return used and unused tubes of the acclimatisation toothpaste to the study site at their Baseline visit (Visit 2). Subjects will bring the used and unused tubes of their assigned study toothpaste to each of their scheduled visits to the study site, per the Schedule of Activities (Table 1-1); all study products will be returned at study conclusion. Study product return will be documented using the study product accountability form/record.

The accountability records must be available for inspection by the study monitor during the study. Monitoring of product accountability will be performed by the monitor during site visits and at the completion of the study.

# 6.4.1 Destruction of Study Product Supplies

At the end of the study, the investigator, or an appropriate designee, and a representative of the sponsor (study monitor) will inventory all used and unused study products and sundry items. The study product accountability record for returned study products will then be completed. All study product (used and unused) for this clinical study, will be returned for destruction to the sponsor's Clinical Supplies Department, or designated vendor, using the return instructions provided.

Detailed instructions for the return of study product/study supplies (including empty tubes) for the accountability checks and subsequent destruction will be provided by the sponsor in time for study close out visit.

Property of GSK Consumer Healthcare - Confidential

May not be used, divulged, published or otherwise disclosed without the consent of GSKCH

CCI Clinical Protocol Template v9.0

Page 32 of 73

# 6.5 Blinding and Allocation/Randomization

All subjects will be centrally randomized to one of the three study toothpastes using an Interactive Response Technology (IRT). Before the study is initiated, training, login information and directions for the IRT will be provided to the study site. Study products will be dispensed according to the instruction received through the IRT at the appropriate study visits.

Returned study products should not be re-dispensed to any subject.

This study is described as examiner-blind (clinical examiners will be blinded to product received). Subjects, site staff, study statistician(s), data management staff, other employees of the Sponsor (including the CRS) and vendors acting on behalf of the sponsor, who may influence study outcomes will also be blinded to product allocation. The monitors and the sponsor's Clinical Study Manager cannot be fully blinded as they will observe subjects brushing with their allocated study product while at the study site. As a matter of study conduct, including emergency unblinding events, only the investigator may learn the contents of one or more of the product codes used to allocate study product, not the clinical examiners. Given the application of IRT within this study, any such knowledge will not affect the decision to enroll a subject or influence the order in which subjects are enrolled.

To ensure the clinical examiners remain blinded throughout the study:

- Site staff involved in the dispensing of study products and supervision of on-site brushing will work in a separate area and will not be involved in any safety or product efficacy assessments.
- Clinical examiners will not be permitted in any area where study product or diaries are stored, dispensed, or in use.
- Subjects will be instructed not to remove their study product or diary from its opaque carrier bag outside of the dispensing room, while at the study site.
- Subjects will be instructed not to discuss which study product they have been assigned or usage instructions with the clinical examiners.

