The age range over which an individual can experience DH is wide (early teens to 70s) (Fischer et al, 1992), with peak incidence known to occur between the ages of 20-40 years (Flynn et al, 1985). The fall in prevalence observed in later decades reflects age-related changes in the dentine and pulp of the tooth which act to reduce both dentine permeability and the tooth's response to external triggers of DH (Pashley, 2008; Seltzer and Bender, 1975). The dental pain experienced by much older members of the population is less likely to be diagnosed as DH (Rees, 2000), thus an age range of 18-70 years has been selected for this study to target individuals with tooth sensitivity due to DH.

While there is no published evidence to indicate that gender impacts the pathophysiology of DH, a national DH survey conducted in rural China in 2009 reported a greater proportion of females with DH compared to males (female 35.8%; male 23.4%) (Liang, 2017). To ensure the current study population is representative of the Chinese population being studied, the study site will aim to recruit a female:male ratio of approximately 3:2.

According to ICH guidelines (ICH E6 (R2) Good clinical practice | European Medicines Agency (europa.eu), for a study to be classed as double blind, the subject, investigator, clinical examiners, monitors, data analysts, and staff involved in determining subject eligibility/ assessing compliance should be blinded to the treatment a subject receives. However, given it will not be possible to ensure identical appearance, flavour and packaging for the three commercial toothpastes to be evaluated in this study, the study is described as 'examiner blind'.

In line with the Chinese MOH guidelines (Ministry of Health (China), 2010) for the testing of functional (desensitising) toothpastes, a regular fluoride toothpaste with no known (or claimed) anti-sensitivity efficacy will be included as the negative control (Crest Cavity Protection Fresh Lime; China commercial product). In addition, a 5.0% CSPS toothpaste (Sensodyne Repair & Protect; China commercial product) with proven DH efficacy in the Chinese population (in

Property of GSK Consumer Healthcare - Confidential

May not be used, divulged, published or otherwise disclosed without the consent of GSKCH

Clinical Protocol Template v9.0

Page 18 of 73

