# 6.7 Compliance

To facilitate compliance with product usage, subjects will be provided with a diary at Screening (Visit 1), at Baseline (Visit 2) and Week 6 (Visit 3) to record each brushing with the acclimatization toothpaste and their assigned study product, respectively.

- The diaries will provide detailed usage instructions for the subject to refer to throughout their participation in the study.
- Subjects will be instructed to note any missed/additional brushings, the reasons for any missed/additional brushings, any issues with the toothpaste used, oral problems, illnesses and any new medications/treatments in their diaries.
- Completed diaries will be reviewed by study staff at the start of each study visit. Any missed or additional brushings will be captured in the eCRF as protocol deviations. Subjects will be re-instructed in correct product usage requirements/diary completion, as needed.

Information recorded in the diary relating to changes in health and medications/ treatments will be reviewed by the investigator, or medically qualified designee, with the subject and transcribed into the eCRF, as appropriate (e.g., as an AE). Information related to product use should also transcribed into the eCRF, as appropriate, taking care to maintain the blind.

Subjects will be instructed to bring all tubes of toothpaste provided (used and unused) to each study visit. Study staff will perform a visual check of product usage. Any suspected over or under use will be documented in the eCRF and the subject will be re-instructed in the correct usage requirements.

To confirm subjects understood the usage instructions provided at Screening (Visit 1), they will be asked to record 2-4 brushings (one per week) during the 2-4 week acclimatisation period using their smartphone video. At Baseline (Visit 2), a designated member of the study team will check these videos to confirm compliance with the usage requirements against a checklist (Appendix 15.3). Any subjects who rinse with water during brushing with the acclimatisation toothpaste will be excluded; subjects deemed non-compliant with any other aspect of study usage requirements will be re-instructed in correct product usage.

Supervised brushings will be carried out at the study site at the end of each study visit to facilitate compliance with usage instructions. If any deviations from per protocol product usage are observed, the subject will be re-instructed of correct product usage.

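### Does Protocol Section 6.5 overstate the masking of subjects and site staff enough to need a change?

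*Protocol*

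**What the plan says.** Section 6.5 opens by calling the study examiner-blind. It then lists "Subjects, site staff, study statistician(s), data management staff, other employees of the Sponsor (including the CRS) and vendors" working for the sponsor, and ends the sentence with "who may influence study outcomes will also be blinded to product allocation". It makes one explicit exception, for the monitors and the Clinical Study Manager, because they watch subjects brush. Section 6.1.2 adds: "Study toothpastes will be dispensed per protocol in blinded fashion to the subject". The same section keeps the dispensing staff away from safety and efficacy assessments and from "any other aspect of the study that could be influenced by knowing which product a subject has been assigned to".

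Section 4.2 gives the reason for the examiner-blind label: "given it will not be possible to ensure identical appearance, flavour and packaging for the three commercial toothpastes". Section 6.1.1 has the tubes over-wrapped "to mask their identity and obscure any branding".

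Conduct differs by arm in three places. Section 4.3 and Table 6-1 give only the test arm the instruction to start with the two test teeth. Footnote 7 of the Schedule of Activities and Section 6.2 have staff point those teeth out to test-arm subjects only. Section 8.2.1.8 sends each subject a brushing video that matches the allocated paste. Tables 6-1 and 6-2 show that the run-in paste and the negative control are the same product with the same brushing instruction.

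**The concern.** Read alone, Sections 6.5 and 6.1.2 promise masking that the design cannot guarantee. Subjects taste and see the paste. A negative-control subject carries on with a product already used for two to four weeks, while a test-arm subject gets a new paste and a new routine. Staff who show the test teeth must know who is in the test arm. If monitors cannot be fully blinded because they watch brushing, the same reasoning applies to the staff who supervise it.

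This could matter because the outcomes come from the subject. The VAS is self-rated, the tactile threshold is a yes/no answer, and the Schiff score (Section 9.1.3) draws partly on what the subject says and does. Examiner blinding protects the scoring but does not remove subject expectation, and Section 4.2 itself says placebo effects are common in this field. A reader who relied on Section 6.5 alone could credit the trial with more protection than it has.

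Two smaller worries sit alongside. Section 7.1 lists unblinding of the subject among the circumstances requiring discontinuation or withdrawal, and its scope might seem unclear if masking is only partial. Arm-specific directions might also appear on the pack or in the diary, since "Each study label will contain, but not be limited to, protocol number, directions for use and storage requirements" and "The diaries will provide detailed usage instructions for the subject to refer to throughout their participation in the study".

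**Working it through.** **1. The plan's own figures.** Inputs from Section 12.1: difference 0.3, SD 0.6, 94 per arm, two-sided 5%, 2% dropout.
- Standard error = 0.6 × √(2/94) = 0.0875. Noncentrality = 0.3 / 0.0875 = 3.43 on 186 degrees of freedom. Noncentral-t power = 92.65%, as stated.
- 235 / 0.98 = 239.8, so 240 randomised, as stated.
- Neither figure uses any assumption about subject masking.

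**2. Reach of the cues.**
- At 2:2:1, 240 × 2/5 = 96 test and 96 negative control; 240 × 1/5 = 48 positive control. The primary comparison uses 96 + 96 = 192 subjects, and 192/240 = 80%.
- Run-in with the negative-control paste: 14 to 28 days × 2 = 28 to 56 brushings. Section 4.3 gives 162 to 178 brushings on treatment.
- 3 measures × 2 visits × 2 comparisons = 12 contrasts (1 primary, 11 secondary). All use subject response wholly or in part.
- The two controls share one instruction, so in the 6 positive-versus-negative contrasts only the paste itself can act as a cue.

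These counts show who meets a cue. They do not show that anyone identifies an arm.

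**3. The passages side by side.**
- *Subjects.* Section 6.5 lists them as blinded, while Section 4.2 says the pastes cannot be matched. Section 6.5 also tells subjects not to discuss their product or their instructions with the examiners, so it already allows that they may know something. The two sections differ in emphasis; neither claims a double-blind study.
- *Dispensing and supervising staff.* The closing clause of the Section 6.5 sentence can be read as limiting the list to those able to affect outcomes. Section 6.1.2 and the first safeguard in Section 6.5 bar these staff from every assessment. Section 6.1.2 openly contemplates that they know the product.
- *Scribe and VAS measurer.* They are not named, but they take part in efficacy assessment. They therefore fall within the limited list, and dispensing or supervising staff cannot fill those roles.
- *Examiners.* Separate areas, opaque bags and a bar on entering places where product or diaries are kept protect them. Nothing in the documents undercuts this.
- *Unblinding in Section 7.1.* Section 6.6 uses the term for breaking the code on a subject's assignment. In a list of withdrawal triggers that is the natural meaning; stretching it to a subject's guess is strained.
- *Label and diary.* The label text is not in the documents, and Section 6.1 refers to a separate packaging and labelling proposal. Whether packs differ by arm cannot be settled from the documents.
- *Monitors.* SAP Section 4.5 calls the site monitors unblinded, where Section 6.5 says not fully blinded. They do not score outcomes, so nothing turns on it.

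**4. What a bias would do, by assumption only.** The documents give no size. Suppose the true effect is zero and expectation shifts the Schiff difference by 0.05, 0.10 or 0.15 points. With 94 per arm and SD 0.6, the chance of a significant result would be 8.8%, 20.6% or 40.0% instead of 5% (smallest significant difference 1.973 × 0.0875 = 0.173). These figures show why subject masking matters in principle. They are not evidence that such a shift exists.

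**5. What rewording would alter.** Each figure in step 4 depends on the pastes and instructions. Rewording Sections 6.5 and 6.1.2 changes neither, so every figure is the same before and after.

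**The case for a change.** The best argument for a change is that the protocol should not state a property the design cannot assure. The limiting clause may cover dispensing staff, but it cannot exempt subjects, whose answers generate the outcomes. By Section 6.5's own reasoning about monitors, subjects and supervising staff should have been excepted too. The cost would be a sentence or two.

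Part of this stands. Subjects are listed as blinded, Section 6.1.2 repeats it, and neither section points back to Section 4.2 or notes that instructions differ by arm. A cross-reference would have been tidier.

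The consequence does not follow. The limitation is disclosed in Section 4.2 as the stated ground for the examiner-blind label, so a reader of the whole protocol is not misled. A cue reveals an arm only to someone who knows which arm carries it. What subjects are told about the arms would be in the consent material, which was not available for this check. The subject-expectation issue belongs in the discussion of results, and report authors can draw it from Section 4.2 without an instruction in the plan.

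**Conclusion.** No change is needed. The mismatch is real but minor: two sections describe subject masking more firmly than Section 4.2 supports. The examiner-blind label is correct, staff who may know the arm are kept out of assessment, and following the plan as written gives exactly the same data and analyses as a reworded plan would. The effect on sample size, power, type I error and estimates is zero.

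Partial subject masking remains a fair point of interpretation for the VAS, the tactile threshold and the subject-response part of the Schiff score. It comes from comparing unmatched commercial products, which the sponsor accepted openly, and wording cannot remove it.

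This conclusion assumes that the Section 6.5 separation of roles is followed, that scribes and VAS measurers are treated as staff able to influence outcomes, and that unblinding in Section 7.1 means the code break in Section 6.6. Whether subjects infer their arm, and with what effect, is not established either way.
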